9.2 First therapy

All patients included, both the first 10 patients and the next 26 patients, will receive bosutinib 400 mg/day in monotherapy during one cycle of treatment. All patients who tolerate this cycle of bosutinib treatment will continue to the second therapy (bosutinib plus atezolizumab).

9.3 Second Therapy

9.3.1 Group 1: The first 10 patients

Only for the first ten patients included in the study, atezolizumab will be introduced at a dose of 840 mg every two weeks combined with 400 mg/day of bosutinib for 2 cycles (8 weeks). These patients will be closely monitored for safety issues.

If dose-limiting toxicities (DLTs) appear in 2 or more patients the study will end.

A DLT would include either of the following adverse events that occurred during bosutinib therapy in combination with atezolizumab, if it is considered at least possibly related to bosutinib and/or atezolizumab:

- Grade 4 neutropenia (<500/ μ l) persisting for > 7 day duration or Grade 4 white cell count decrease for >7 day duration (<1000/ μ l).
- Febrile neutropenia (ANC<1000/ μ l and fever \geq 38.5°C).

- Grade 4 thrombocytopenia > 48 hour duration or with bleeding requiring platelet transfusion.
- Any Grade 3 or 4 clinically evident non-hematological toxicity.
- Any ≥Grade 3 toxicity that requires >14 days to resolve (to ≤Grade 1 despite optimal medical therapy).

DLTs will be graded according to the NCI CTCAE, v5.0.

If no relevant safety issue, regarding the combination is detected the study will continue.

These initial 10 patients will cross-over from bosutinib 400 mg/day plus atezolizumab 840 mg every 2 weeks to bosutinib 400 mg/day plus atezolizumab 1680 mg every 4 weeks for 10 cycles (40 weeks).

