9.1 Patient Screening

This study will be conducted on those naïve patients with chronic-phase Chronic Myeloid Leukemia (CP-CML) who meet the established selection criteria (see below). The patients that sign the IC and meet the selection criteria will be selected to enter the study.

Results of all screening evaluations must be reviewed by the Principal Investigator or his/her designee prior to the enrollment of a patient into the study to assure that all inclusion and none exclusion criteria have been satisfied.

All study patients must be thoroughly informed about all aspects of the study, including the study visit schedule and required assessments for informed consent. The written informed consent must be obtained prior to any screening evaluations. If a patient is unable to read, an impartial witness should be present during the entire informed consent discussion.

This is an open label clinical trial, and no randomization or blinding procedures are required.

The patients will be divided in two groups, with different start points, and will have three different therapy combinations during the study, which are described below. The first 10 patients included in the study will begin first. If at least 9 of these patients do not suffer DLTs during the first 2 cycles of the combined treatment (bosutinib 400 mg/day plus atezolizumab 840 mg every two weeks), the following 26 patients will be included, otherwise, the study will be terminated.

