9.5 Withdrawal criteria

Patients may suspend their participation in the study whenever they wish, based on his/her own judgement and opinion, without giving any explanation, although the investigator may investigate the reasons of a voluntary dropout.

The investigator may also decide to withdraw a patient from the trial if he/she does not comply with the protocol, due to AEs or treatment inefficacy or toxicity.

Patients who do not comply with at least 70% of the scheduled doses of bosutinib or that, in 4 or more times, the administration of atezolizumab is cancelled, will be withdrawn from the study.

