11.6 Dose Modification and Dose Delay

The following section summarizes dosing modifications of bosutinib or atezolizumab to manage possible toxicity. Administration of bosutinib or atezolizumab could be stopped for an individual subject in the event of a treatment-related toxicity that, in the Investigator's assessment, warrants discontinuation. Exceptions to these guidelines will require approval from the Medical Monitor.

A maximum discontinuation of 1 month is allowed for the treatment with bosutinib if required due to the onset of adverse events, investigator decision, or other major circumstances. If a subject discontinued treatment for more than one month he/she will be withdrawn from the study and the appropriate follow-up procedures will be conducted. Also, to be included in the

efficacy analysis (Per protocol set population), a subject must comply with at least 70% of treatment with bosutinib. Regarding atezolizumab treatment, fail to administrate up to 3 out of the 11 administrations scheduled, will be allowed to continue in the study. If, for any reason, atezolizumab could not be administered 4 or more times during the course of the study, the subject will be withdrawn from the study and the appropriate follow-up procedures will be conducted. All deviations from the scheduled treatments regime shall be recorded in the patients' clinical history and the eCRF and explained if required.

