11.6.2.2 Hepatic Events

Immune-mediated hepatitis has been associated with the administration of atezolizumab. Eligible subjects must have adequate liver function, as manifested by measurements of total bilirubin and hepatic transaminases, and liver function will be monitored throughout study treatment.

While in this study, subjects who present with right upper-quadrant abdominal pain or unexplained nausea or vomiting should have liver function tests (LFTs) performed immediately and reviewed before administration of the next dose of study drug.

If LFTs worsened, concurrent medications, viral hepatitis, and toxic or neoplastic etiologies should be considered and addressed, as appropriate.

For specific management guidelines please see Table 4.

Table 4. Management Guidelines for Hepatic Events

Adverse Event	Management
Hepatic event, Grade 1	
Continue atezolizumab.Monitor LFTs until values resolve to within normal limits.
Hepatic event, Grade 2	All events:

Adverse Event	Management
	
Monitor LFTs more frequently until return to baseline values. 
Events of >5 days' duration:
 
Withhold atezolizumab for up to 12 weeks after event onset.^aInitiate treatment with 1-2 mg/kg/day oral prednisone or equivalent.If event resolves to Grade 1 or better, resume atezolizumab.^bIf event does not resolve to Grade 1 or better while withholding atezolizumab, permanently discontinue atezolizumab and contact
Hepatic event, Grade 3 or 4	
Permanently discontinue atezolizumab and contact the Sponsor.^cConsider subject referral to gastrointestinal specialist for evaluation and liver biopsy to establish etiology of hepatic injury.Initiate treatment with 1-2 mg/kg/day oral prednisone or equivalent.If event does not improve within 48 hours after initiating corticosteroids, consider adding an immunosuppressive agent.If event resolves to Grade 1 or better, taper corticosteroids over ≥1 month.

LFT =liver function tests.

- Atezolizumab may be withheld for a longer period (ie, > 12 weeks after event onset) to allow for corticosteroids (if initiated) to be reduced to ≤10 mg/day oral prednisone or equivalent. The acceptable length of the extended period must be agreed upon by the investigator and the Sponsor.

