11.6.2.9 Neurologic Disorders

Myasthenia gravis, Guillain-Barré syndrome, and meningoencephalitis have been observed with single agent atezolizumab. Subjects may present with signs and symptoms of sensory or motor neuropathy. Diagnostic work-up is essential for an accurate characterization to differentiate between alternate etiologies. For specific management guidelines please see Table 11.

Table 11. Management Guidelines for Neurologic Disorders, Including Meningoencephalitis

Adverse Event	Management
Immune-related neuropathy, Grade 1	
Continue atezolizumab.Investigate etiology.
Immune-related neuropathy, Grade 2	
Withhold atezolizumab for up to 12 weeks after event onset.^aInvestigate etiology.Initiate treatment as per institutional guidelines.If event resolves to Grade 1 or better, resume atezolizumab.^bIf event does not resolve to Grade 1 or better while withholding atezolizumab, permanently discontinue atezolizumab and contact the sponsor
Immune-related neuropathy, Grade 3 or 4	
Permanently discontinue atezolizumab and contact the Sponsor.^cInitiate treatment as per institutional guidelines.

Adverse Event	Management
Myasthenia gravis and Guillain-Barré syndrome (any grade)	
▪ Permanently discontinue atezolizumab and contact the Sponsor.^c▪ Refer subject to neurologist.▪ Initiate treatment as per institutional guidelines.▪ Consider initiation of 1-2 mg/kg/day oral or IV prednisone or equivalent.
Immune-related meningoencephalitis, all grades	
▪ Permanently discontinue atezolizumab and contact the Sponsor.^c▪ Refer subject to neurologist.▪ Initiate treatment with 1-2 mg/kg/day IV methylprednisolone or equivalent and convert to 1-2 mg/kg/day oral prednisone or equivalent upon improvement.▪ If event does not improve within 48 hours after initiating corticosteroids, consider adding an immunosuppressive agent.▪ If event resolves to Grade 1 or better, taper corticosteroids over ≥ 1 month.

IV=intravenous

- a. Atezolizumab may be withheld for a longer period of time (ie, >12 weeks after event onset) to allow for corticosteroids (if initiated) to be reduced to ≤ 10 mg/day oral prednisone or equivalent. The acceptable length of the extended period of time must be agreed upon by the investigator and the Sponsor.

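### The DLT list has no item for permanent discontinuation, so Grade 1-2 myasthenia gravis, Guillain-Barré syndrome or meningoencephalitis can stop atezolizumab for good without counting as a DLT.

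*Protocol*

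**What the plan says.** The DLT list is the same in the Protocol Synopsis, Protocol 9.3.1 and SAP 4.1. It has five items, and three are hematological. The other two are "Any Grade 3 or 4 clinically evident non-hematological toxicity" and a duration item for toxicity of Grade 3 or higher that takes more than 14 days to settle to Grade 1 or below. All require at least a possible relation to either drug. None mentions discontinuation, and *clinically evident* is not defined.

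The count drives the main decision of the phase Ib part. Protocol 9.1 admits the next 26 patients on this condition: "If at least 9 of these patients do not suffer DLTs during the first 2 cycles of the combined treatment". Otherwise the study ends.

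The management tables use a different threshold. In Table 11 (Protocol 11.6.2.9), the rows headed "Myasthenia gravis and Guillain-Barré syndrome (any grade") and "Immune-related meningoencephalitis, all grades" both require permanent discontinuation of atezolizumab. Footnote c allows rechallenge after full recovery if the investigator and sponsor approve. In Table 4 (Protocol 11.6.2.2), the row for Grade 3 or 4 hepatic events says "Permanently discontinue atezolizumab and contact the Sponsor", with no condition on duration.

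Missed doses lead to withdrawal. Protocol 9.5 says of such patients: "in 4 or more times, the administration of atezolizumab is cancelled, will be withdrawn from the study". Protocol 11.6 repeats the rule: "atezolizumab could not be administered 4 or more times during the course of the study, the subject will be withdrawn from the study".

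**The concern.** A DLT count should pick up toxicity that makes the combination undeliverable. Here the protocol treats three neurologic diagnoses as serious enough to end atezolizumab whatever their grade, but the DLT list recognises non-hematological toxicity only from Grade 3. A patient can lose the experimental drug, and then the study, because of related immune toxicity and still support the statement that the combination was tolerated.

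With a threshold of two patients, one uncounted patient can reverse the group 1 decision. Safety is the primary objective, and that decision exposes up to 26 more newly diagnosed patients to the combination.

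**Working it through.** **Plan's own figure.** The only figure derived in the sample-size section is 30-31 patients on the combination: 36 × (1 − 0.15) = 30.6, which agrees. The point does not depend on it. No DLT rate, target rate or error rate is stated.

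**Step 1. A related Grade 1-2 neurologic case against each DLT item.**

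| DLT item | Met? |
|---|---|
| Prolonged Grade 4 neutropenia or white cell decrease | No, hematological |
| Febrile neutropenia | No, hematological |
| Grade 4 thrombocytopenia, prolonged or with bleeding | No, hematological |
| Grade 3-4, clinically evident, non-hematological | No, grade too low |
| Grade 3 or higher, over 14 days to resolve | No, grade too low |

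No item is met, yet Table 11 requires a permanent stop. This conclusion needs no assumption.

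**Step 2. Does withdrawal follow?** Table 14 schedules group 1 doses on D29, D43, D57 and D71 (4 at 840 mg), then every 28 days from D85 to D337: (337 − 85)/28 + 1 = 10 at 1680 mg. The total is 14. A stop before D85 misses at least 10, against a limit of 4. Protocol 11.6 speaks of 11 scheduled administrations, which matches neither Table 14 nor the 12 in Table 16. Even on a base of 11, with 4 already given, 7 are missed. Withdrawal follows unless rechallenge is approved early enough.

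**Step 3. Effect on the count.** With one DLT as written plus one such case, the count is 1 and the study continues. If the case counted, it would be 2 and the study would end. With two such cases, the count is 0 as written and 2 if counted.

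**Step 4. The hepatic route.** A Grade 3-4 hepatic event with symptoms meets the fourth item however short it is. To escape, an event must be laboratory-only, return to Grade 1 or less within 14 days, and occur under a reading of *clinically evident* that excludes laboratory findings. It must also be detected, since an unseen event stops nothing. Group 1 chemistry is scheduled on D29, before the first atezolizumab dose, and on D85, with none between (Table 14; Protocol 12.15.2). If onset were uniform over those 56 days (an assumption), the D85 sample would catch an event of at most 14 days in at most 14/56 = 25% of cases. Table 4 does foresee quick recovery without a restart: "If event resolves to Grade 1 or better, taper corticosteroids over ≥1 month".

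**Step 5. Group 2.** Two DLTs move all patients from 1680 mg every 4 weeks to 840 mg every 2 weeks. Per 28-day cycle that is 2 × 840 = 1680 mg, so the total is unchanged.

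**Step 6. Illustration only.** With 10 evaluable patients and a per-patient rate r, P(2 or more) = 1 − (1 − r)^10 − 10r(1 − r)^9. At r = 0.10 this is 1 − 0.349 − 0.387 = 0.264. Let p be the DLT rate as written and q an added rate for cases now uncounted, so r = p + q. Both are assumed.

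| p | q = 0 | q = 0.01 | q = 0.02 | q = 0.05 |
|---|---|---|---|---|
| 0.05 | 0.086 | 0.118 | 0.152 | 0.264 |
| 0.10 | 0.264 | 0.303 | 0.342 | 0.456 |
| 0.20 | 0.624 | 0.654 | 0.682 | 0.756 |

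The chemistry detection factor in step 4 is not applied here, because neurologic events are not found by chemistry.

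**The case against.** The strongest reply is that patients are protected without the DLT label. Tables 4 and 11 stop the drug and bring in the sponsor, the medical monitor reviews safety data (Protocol 16), and the sponsor may terminate for doubtful safety (Protocol 18.7). All of this applies to both groups. In group 1, Protocol 9.3.1 also ties continuation to the absence of a relevant safety issue. This stands. A reader might infer that the next 26 patients enrol automatically after an uncounted event, and the documents do not support that. The safeguards rest on judgement, however, and none changes the count.

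A second reply is that nothing obliges a sponsor to make discontinuation a DLT. That is true; this is a design choice. The difficulty is that the protocol's own tables and its DLT list treat the same event differently.

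A third is that the list's opening wording is loose enough to admit other events. The amendment log for version 1.2 records that investigator discretion was taken out of the definition to remove subjectivity, so an open-ended reading would undo that change. The same history argues against a broad item for all immune-mediated discontinuations: with both drugs on board, attributing a transaminase rise to one of them is itself a judgement.

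Two stronger readings fail. A reader might infer that any brief Grade 3-4 hepatic event escapes; symptomatic ones already count. A reader might also infer that group 2 stays on a higher dose because events go uncounted; the rule there changes only the schedule.

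**Conclusion.** The point holds for the neurologic events without conditions: a related Grade 1-2 case of the three named diagnoses is not a DLT, although the protocol requires a permanent stop and, without rechallenge, withdrawal. It holds for hepatic events only in the narrow laboratory-only case, and only on one reading of an undefined term.

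The consequence lies mainly in the group 1 stop rule. The certain part is that one counted DLT plus one such patient stays below the threshold of 2. The probability of that happening cannot be obtained from the documents. The table in the working is a set of assumptions, and a reader should not take it as an estimate of how often the study would wrongly continue. With partial safeguards in place, this is an inexpensive improvement to the definition. It is not evidence that the safety monitoring fails.

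**What to change.** Add one item to the DLT list in the Synopsis, Protocol 9.3.1 and SAP 4.1: *any at least possibly related myasthenia gravis, Guillain-Barré syndrome or immune-related meningoencephalitis, of any grade, for which Table 11 requires permanent discontinuation of atezolizumab, regardless of duration or later rechallenge*. Naming diagnoses keeps the item objective and avoids the attribution problem with transaminases.

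In the same places, state whether a Grade 3-4 hepatic abnormality seen only in the laboratory is clinically evident. Either answer removes the ambiguity. If the answer is yes, scheduled sampling still limits what can be counted in group 1, because no chemistry is planned between D29 and D85.

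The cost is wording in two documents and a slightly higher chance of ending the study in group 1, where there is no de-escalation step. The size is unknown without rates. The sponsor should confirm that 2 of 10 is still the intended threshold once the item is added.

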9.3.2 Group 2: The next 26 patients

After receiving bosutinib 400 mg/day in monotherapy for one cycle (1st therapy), the last 26 patients included will receive bosutinib 400 mg/day plus atezolizumab 1680 mg every 4 weeks for 12 cycles.

Patients will continue to be closely monitoring. If DLTs appear in 2 or more patients at a dose of 1680 mg of Atezolizumab every 4 weeks, the dose of atezolizumab will be reduced for all patients to an 840 mg Atezolizumab every 2 weeks dose.

All patients completing 12 treatment cycles (48 weeks) will begin the last therapy of study.

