- after prior platinum containing chemotherapy, or
- who are considered cisplatin ineligible, and whose tumours have a PD-L1 expression ≥ 5%.

Also, in combination with bevacizumab, paclitaxel and carboplatin, atezolizumab is indicated for the first-line treatment of adult patients with metastatic non-squamous non small cell lung cancer (NSCLC). In patients with EGFR mutant or ALK-positive NSCLC, atezolizumab, in

combination with bevacizumab, paclitaxel and carboplatin, is indicated only after failure of appropriate targeted therapies.

Atezolizumab as monotherapy is indicated for the treatment of adult patients with locally advanced or metastatic NSCLC after prior chemotherapy. Patients with EGFR mutant or ALK positive NSCLC should also have received targeted therapy before receiving atezolizumab.

Atezolizumab at a dose of 1–20 mg/kg produced a dose-proportional increase in exposure to the drug. Typical clearance was 0.20 L/day, volume of distribution at steady state was 6.9 L, and the terminal half-life was 27 days, according to a population analysis of patients in the dose range (n = 472). This population analysis also suggested steady state occurs after 6–9 weeks treatment (2–3 dosage cycles). Systemic accumulation in terms of area under the plasma concentration time curve (AUC), maximum concentration (C_{max}) and trough concentration (C_{min}) was 1.91, 1.46 and 2.75-fold, respectively. The systemic exposure to atezolizumab was not significantly affected when analysed according to patient age, body-weight, gender, positive anti-therapeutic antibody status, albumin levels, tumour burden, region or race, mild or moderate renal impairment, mild hepatic impairment, level of PD-L1 expression, or Eastern Cooperative Oncology Group (ECOG) performance status. The potential for atezolizumab to interact with other drugs is unknown (*Markham, 2016; EMA, 2019*).

Major common AEs involved fatigue, decreased appetite, nausea, diarrhea, pyrexia, pruritus, cough, edema peripheral, and rash. The most common severe AEs were fatigue, anemia, and dyspnea. The overall atezolizumab-related death rate was much lower than chemotherapeutics-related death rate. Atezolizumab has better overall survival and lower risk of AEs compared with chemotherapy (*Tie, 2019*).

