11.5 Treatment Duration

The patients included will remain in the study for at least 100 weeks, 4 weeks (1 cycle) in the first treatment phase, 48 weeks (12 cycles) in the second treatment phase, and 48 weeks (12 cycles) in the third treatment phase), unless discontinue early.

The First 10 Patients:

- First cycle, they will receive bosutinib 400 mg/day in monotherapy.
- Second and third cycles, they will receive bosutinib 400 mg/day in combination with atezolizumab 840 mg every two weeks.
- If no safety issues are detected, these patients will cross-over from bosutinib 400 mg/day plus atezolizumab 840 mg every 2 weeks to bosutinib 400 mg/day plus atezolizumab 1680 mg every 4 weeks for 10 more cycles.
- After 12 cycles of treatment with bosutinib plus atezolizumab combination, the patients will continue with bosutinib 400 mg/day in monotherapy for 12 more cycles.

Other 26 Patients:

- First cycle, they will receive bosutinib 400 mg/day in monotherapy.
- Second cycle, they will receive bosutinib 400 mg/day plus atezolizumab 1680 mg every 4 weeks for 12 cycles.
- After 12 cycles of treatment with bosutinib plus atezolizumab combination, the patients will continue with bosutinib 400 mg/day in monotherapy for 12 more cycles.

If, at any point during the treatment with bosutinib 400 mg/day plus atezolizumab 1680 mg every 4 weeks, 2 or more patients experience DLTs, atezolizumab dosage will change to 840 mg every 2 weeks.

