11.6.2 Dose reduction steps for atezolizumab

Although most immune-mediated adverse events observed with immunomodulatory agents have been mild and self-limiting, such events should be recognized early and treated promptly to avoid potential major complications. Discontinuation of atezolizumab may not have an immediate therapeutic effect and, in severe cases, immune-mediated toxicities may require acute management with topical corticosteroids, systemic corticosteroids, or other immunosuppressive agents.

The investigator should consider the benefit-risk balance a given subject may be experiencing prior to further administration of atezolizumab. Atezolizumab should be permanently discontinued in subjects with life-threatening, immune-mediated adverse events. Specific guidelines for immune-mediated events are provided in Tables 3 to 13.

For all other non-immune mediated adverse events, including infections, atezolizumab should be withheld for Grade 3 or higher toxicity with the following exceptions:

- Grade 3 nausea that responds to antiemetic treatment within 7 days
- Grade 3 vomiting that responds to antiemetic treatment within 7 days
- Grade 3 diarrhea that responds to antidiarrheal treatment within 7 days
- Grade 3 fatigue that was present at baseline or that lasts for <7 days after the last administration of atezolizumab
- Grade 3 asthenia that was present at baseline or that lasts for <7 days after the last administration of atezolizumab

Administration of atezolizumab may be restarted upon recovery from toxicity to Grade 1 or baseline.

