12.19 Adverse Events and Concomitant Medications

AEs and concomitant medications will be recorded continuously throughout the study, starting on the date of the first administration of the study medication, and, at least, up to the 28-day follow-up visit after the last dose of treatment. New and updated AEs and concomitant medications will be reported within the treatment period; ongoing AEs thought to be at least possibly study-drug related; and all ongoing SAEs should be followed at least every 4 weeks until they resolve to baseline (or to NCI CTCAE, v5.0 grade ≤ 1), stabilize, or are considered to be chronic/irreversible (see section 13 Adverse Events reporting, for more information). Those relevant events that start before the first administration of the study drug will be recorded in the clinical history of the subject.

A maximum discontinuation of 1 month is allowed for the treatment with bosutinib if required due to the onset of adverse events, investigator decision, or other major circumstances. If a subject discontinued treatment for more than one month he/she will be withdrawn from the study and the appropriate follow-up procedures will be conducted. Regarding atezolizumab treatment, fail to administrate up to 3 out of the 11 administrations scheduled will be allowed for a patient to continue in the study. If, for some reasons, atezolizumab could not be administered 4 or more times, during the course of the study, the subject will be withdrawn from the study and the appropriate follow-up procedures will be conducted. All deviations from the scheduled treatments regime shall be recorded in the patients' clinical history and the eCRF and explained if required.

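### After 2 DLTs on 1680 mg every 4 weeks, atezolizumab is 'reduced' to a schedule with the same total dose per 4 weeks, and no cohort DLT count follows the switch

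*Protocol*

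**What the plan says.** Group 2 receives 1680 mg on day 1 of each 28-day cycle. Once 2 or more patients have a DLT on that schedule, Protocol 9.3.2, the synopsis and SAP 4.1 all state that "the dose of atezolizumab will be reduced for all patients to an 840 mg Atezolizumab every 2 weeks dose". Protocol 11.5 gives the same rule, applying at any point on 1680 mg every 4 weeks, but calls it a change: if "2 or more patients experience DLTs, atezolizumab dosage will change to 840 mg every 2 weeks". None of these places gives a further step.

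For Group 1, which starts on 840 mg every 2 weeks, Protocol 9.3.1 sets a hard stop: "If dose-limiting toxicities (DLTs) appear in 2 or more patients the study will end". Protocol 9.1 gives its scope. Group 2 opens "If at least 9 of these patients do not suffer DLTs during the first 2 cycles of the combined treatment"; otherwise the study is terminated. SAP 4.1 repeats the DLT rules, and SAP 4.4 plans no interim analysis.

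**The concern.** A reader who sees that the dose is reduced after DLTs expects patients to receive less drug. Here they receive the same amount, split differently. The schedule they move to is the one on which 2 DLTs in 10 patients would have ended the study, yet once patients have been moved there because of DLTs, the plan has no count at which anything further happens.

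Safety is the primary objective, and the switch is the only pre-specified numeric cohort response to DLTs on 1680 mg every 4 weeks. If DLTs continue, stopping atezolizumab for the cohort rests on sponsor judgement under Protocol 18.7. Patients who start atezolizumab after the switch are as new to the combination as the Group 1 patients were, but have no equivalent limit.

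**Working it through.** **Inputs.** Doses, intervals, trigger and Group 1 gate: Protocol 9.1, 9.3.1, 9.3.2, 11.1, 11.5. Pharmacokinetics (Protocol 6.3): "Typical clearance was 0.20 L/day, volume of distribution at steady state was 6.9 L, and the terminal half-life was 27 days". Loss before the combination, at most 15% of 36: Protocol 15.5. The documents give no DLT rate, so two-cycle risks of 10%, 20% and 30% are assumed.

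**1. The plan's own figures.** 36 × 0.85 = 30.6, matching the stated 30-31 patients on the combination. For Group 2, 26 × 0.85 = 22.1. At least 9 of 10 without a DLT is the same rule as stopping at 2 of 10, so Protocol 9.1 and 9.3.1 agree.

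**2. Dose and AUC.** Per 28 days: 1 × 1680 = 1680 mg before and 2 × 840 = 1680 mg after. Steady-state AUC = dose/clearance = 1680/0.20 = 8400 mg·day/L on both.

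**3. Peak and trough.** One compartment at steady state, k = ln 2/27 per day, V = 6.9 L. Peak = (dose/V)/(1 − exp(−k × interval)); trough = peak × exp(−k × interval).
- 1680 mg every 28 days: peak 475, trough 231 mg/L.
- 840 mg every 14 days: peak 403, trough 281 mg/L.
- Ratios: peak 0.849, trough 1.216.

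Using k = 0.20/6.9 instead, the peak falls about 17% and the trough rises about 25%. The direction is the same.

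**4. What Group 1 clearance shows.** One-sided exact 95% upper bound on the DLT risk: 0/10 gives 25.9%; 1/10 gives 39.4%.

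**5. How often a further limit would matter for patients already treated.** The plan has no limit after the switch, so an illustrative one is needed: DLTs in 20% of the N patients on atezolizumab at the switch, within 2 cycles. The table assumes that they carry the two-cycle risk again after the switch.

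| Probability | 10% | 20% | 30% |
|---|---|---|---|
| Group 1 gate passes, ≤1 of 10 | 0.736 | 0.376 | 0.149 |
| Trigger fires, ≥2 of 22 | 0.661 | 0.952 | 0.996 |
| Limit met, ≥4 of N = 20 | 0.133 | 0.589 | 0.893 |
| Product of the three | 0.065 | 0.211 | 0.133 |

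With 22 or 26 Group 2 starters and N = 20 or 30, the products are 4-7%, about 21% and 13-14%. At 5% risk they are about 0.5% or less. A simulation in time order (22 starts spread over 9 cycles, an assumption) gives 4.7%, 18.2% and 12.2%. If all risk is spent in each patient's first 2 combination cycles, it gives about 0.2% or less.

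**6. Later starters.** Under the same spread of starts, when the trigger fires the median number of Group 2 patients who have not yet started atezolizumab is 7, 11 and 14 of 22 at 10%, 20% and 30% risk. Their first-cycles risk does not depend on recurrence. A limit of 2 DLTs in 10 such patients would be reached with probability 26%, 62% and 85%, the same as the Group 1 gate. Under the present text the probability that a cohort count acts is zero.

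**The case against.** The strongest defence is that the switch returns everyone to a schedule that has passed a safety run-in. That stands as a reasonable choice. The documents give no relation between exposure and toxicity, so the lower peak may or may not help. Dose and interval are stated wherever the rule appears, so the wording should not cause a dosing error, and *reduced* is true of each infusion.

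The Group 1 comparison is not exact. That gate covers the first 10 patients in their first 2 combination cycles on 840 mg every 2 weeks. Switched patients may have months of exposure behind them. The comparison is closest for later starters.

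A reader might infer that nothing protects patients after the switch. The documents do not support that. For adverse events that are not immune-mediated, "atezolizumab should be withheld for Grade 3 or higher toxicity with the following exceptions". Protocol 11.6.2 also has discontinuation tables for immune-mediated events. "AEs and concomitant medications will be recorded continuously throughout the study" (Protocol 12.19), SAEs and AESIs go to the sponsor within 24 hours (13.4), the medical monitor reviews safety data (16), and the sponsor may terminate for questionable safety (18.7). These measures act on individuals or are discretionary. None is a cohort DLT count.

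Leaving a second cohort stop to judgement is tenable in a 36-patient exploratory study. A mandatory stop would also have a cost. The FAS requires successful completion of the combination (Protocol 4 and 15.1.1, SAP 6.2) and the PPS is a subset of it, so a cohort stop would push patients out of both. This favours a pause and review over an automatic stop.

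**Conclusion.** The point holds. The switch leaves dose and AUC per 4 weeks unchanged, which needs no assumption beyond the protocol's own figures, and no cohort DLT count follows it. The peak and trough changes rest on a one-compartment model.

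The benefit of adding a count is uncertain. For patients already treated it runs from practically nil to about 20% of trials at an assumed 20% two-cycle risk, depending on whether risk recurs after the switch, and the documents settle neither case. The 20% threshold behind those figures is illustrative. The case is clearer for later starters, whose exposure is new.

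Two stronger readings are not supported. One is that the return to 840 mg every 2 weeks is wrong in itself: it is the only schedule with a completed run-in. The other is that 2 DLTs on 1680 mg every 4 weeks should end the study: the Group 1 stop was not written for that schedule, and the trigger of 2 is not in question. This is a cheap improvement for patient safety.

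**What to change.** Amend Protocol 9.3.2, 11.5, the synopsis and SAP 4.1, keeping the trigger of 2.

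1. Wording: *changed to 840 mg every 2 weeks (same total dose per 4 weeks)*.
2. Add a post-switch DLT count in two parts: switched patients, for 2 cycles from the switch; and every patient who first starts atezolizumab after it, for the first 2 combination cycles. Count later starters separately against a limit comparable to the Group 1 gate, for example 2 DLTs among the first 10. The sponsor sets the limit for switched patients.
3. When a limit is reached, new atezolizumab starts pause. A documented review by the sponsor and medical monitor decides whether atezolizumab continues, before any further patient starts.
4. If atezolizumab is stopped for the cohort, patients continue bosutinib with follow-up and are not removed from the efficacy sets because of that stop. The missed infusions do not count under the rule that if "atezolizumab could not be administered 4 or more times during the course of the study, the subject will be withdrawn from the study" (Protocol 11.6; also 9.5 and 12.19).
5. Take vital signs before infusion at the extra day-15 visits. The note above Table 14 in Protocol 12.1 now limits these visits to giving the drug, whereas Protocol 12.9 has day-15 vital signs for Group 1 in cycles 2 and 3.

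**Cost.** A short paragraph in each document, an adjustment to the efficacy-set definitions, and no extra patients or visits. The downside is an unneeded pause at an acceptable DLT rate: 26% at a 10% risk for 2 in 10, as in Group 1, and less if fewer than 10 later starters remain. It is higher if the switched-patient count is also checked. With the illustrative 20% limit, recurring risk and independent counts, it is 1 − 0.736 × 0.867 = 36% (N = 20) or 1 − 0.736 × 0.927 = 32% (N = 30).
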